4.3. Study Procedures

Table 1 presents the visit schedule and procedures to be conducted at each visit.

Table 1: SCHEDULE OF PROCEDURES

Study Period Study Day	Screening/ Enrollment	Randomization	Treatment	Monitoring Period			Follow-Up Period			ET
	Up to Day -14 ^a	Day 1 pre-dose	Day 1	Day 2/3 ^b (BAL PK sub-study)	Day 2 to Day 21 ^c	Day 22 (+2 days)	Day 28 (+2 days) ^d	Day 40 to Day 89 ^e	Day 90 (±7 days) Safety Visit ^f	Unsched ^g
Study Procedures										
Informed consent	X									
Inclusion/exclusion/ randomization criteria	X ^{h,i}	X ^j								
Medical history	X ^h	X ^k								
Demographics	X ^h									
Antibiotic/medication history ^l	X	X								
Height/weight	X ^h									
Physical examination ^m	X ^h	X			X	X		X	X	X
Vital signs ⁿ	X ^h	X	X	X	X	X		X	X	X
Pregnancy test ^o	X ^h					X				X
Clinical laboratory assessments (chemistry, hematology, and coagulation)		X			X ^p	X				X ^q
Urinalysis		X			X ^r	X				X ^q
Procalcitonin (analysis performed at central lab)		X			X ^s	X				X
Ventilator device status	X	X	X	X	X ^t	X ^t	X ^t	X ^t	X ^t	X ^t
Chest X-ray/thoracic CT scan	X ^u	X ^v		X	X ^w	X ^w				
Nasal swab specimens for culture		X								
ETA for culture ^x	X									
Collection/culture of additional microbiological specimens ^y					X	X				X
Clinical assessment of signs/symptoms of pneumonia		X	X	X	X	X				X
Other S. aureus infection assessment	X	X	X	X	X	X				X

Footnotes begin on the next page.

Table 1: SCHEDULE OF PROCEDURES (Continued)

Study Period Study Day	Screening/ Enrollment	Randomization	Treatment	Monitoring Period			Follow-Up Period			ET
	Up to Day -14 ^o	Day 1 pre-dose	Day 1	Day 2/3 ^b (BAL PK sub-study)	Day 2 to Day 21 ^c	Day 22 (+2 days)	Day 28 (+2 days) ^d	Day 40 to Day 89 ^e	Day 90 (±7 days) Safety Visit ^f	Unsched ^g
Study Procedures										
Randomization		X								
Blood collection for ADA and anti- S. aureus toxin antibodies		X			X ^z	X		X	X	X
12-lead ECG		X				X		X	X	X
Assess survival and discharge disposition						X	X	X	X	X
Study drug administration ^{aa}			X							
BAL for PK ^{bb}				X						
Blood collection for PK sampling and anti- S. aureus toxin antibodies			X ^{cc}	X ^{dd}	X ^{ee}	X ^{ee}		X ^{ee}	X	X
Track days on ventilator from randomization			X	X	X	X		X	X	X
Track days in ICU (or other observation area)			X	X	X	X		X	X	X
Concomitant medications ^l		X	X	X	X	X		X	X	X
Adverse event assessment	X ^{ff}	X	X	X	X	X		X	X	X

- a. Eligible subjects will be screened daily (while mechanically ventilated) for up to 8 days to identify those subjects who are heavily colonized with *S. aureus* (see Protocol Section 3.1). Screening for heavy *S. aureus* colonization by ETA culture will continue on Day 11 and Day 14 provided the subject remains mechanically ventilated, for a total Screening Period of up to 14 days. Additional ETA screening may occur on Days 9, 10, 12, and 13 at the discretion of the Investigator and providing the subject remains mechanically ventilated.
- b. Procedures are to be performed 48 hours (±36 hours) post-dose on approximately Day 2 or Day 3, depending on time of study drug administration, for those subjects participating in the BAL fluid PK sub-study only or if BAL fluid is collected as part of a standard of care procedure for any subject at any other time post-randomization for any other reason.
- c. Procedures are to be performed daily (unless otherwise indicated) from Day 2 to Day 21 while the subject is hospitalized. For subjects participating in the BAL fluid PK sub-study, procedures noted for the Day 2 visit only need to be performed 1 time.
- d. A follow-up visit will occur on Day 28 (+2 days) to assess mortality. This visit may be conducted via telephone if the subject is no longer hospitalized.
- e. For subjects who remain hospitalized between Day 40 and Day 90 at the institution where they receive study treatment, a follow-up safety visit will be performed on the day of discharge.
- f. If the subject is unable to return to the site, this visit may be conducted by telephone, with procedures performed as appropriate (i.e., concomitant medications and adverse events collected).
- g. An ET visit will be conducted for subjects who are withdrawn from the study prior to Day 22.

- h. To be performed at the initial Screening Visit only.
- i. At the Screening Visit, subjects must meet all of the inclusion criteria and none of the exclusion criteria in order to be eligible to return for the Randomization Visit.
- j. At the Randomization Visit, subjects must continue to meet all of the inclusion criteria and none of the exclusion criteria. Subjects must also meet all randomization criteria to be eligible to be randomized into the study.
- k. Review and record medical history (if changes occurred since the Screening Visit).
- l. All prior medications received by the subject within 14 days prior to study drug administration and any concomitant medications used throughout the duration of the study will be recorded in the source documents and on the appropriate eCRF.
- m. A complete physical examination will be performed at the Screening Visit and as deemed necessary by the Investigator and will include, at a minimum, a pulmonary examination (including auscultation) and assessments of the skin, abdomen, cardiovascular, gastrointestinal, and neurological systems. A limited physical examination will be performed at the Randomization Visit, daily during the Monitoring Period (if the subject is hospitalized), on Day 22 (if the subject is hospitalized), at the time of hospital discharge (if discharge occurs between Day 40 and Day 90), at the Safety Visit (Day 90) if the visit occurs onsite, and at ET (if applicable). The limited physical examination will include, at a minimum, a pulmonary examination (including auscultation).
- n. Vital sign measurements will include temperature, systolic and diastolic blood pressure, pulse, respiratory rate, and oxygenation status. Blood pressure and pulse will be assessed via an automated device. Manual techniques are only to be used if an automated device is not available. Oxygenation status will be determined via measurement of arterial blood gas, provided the subject has an arterial line placed. If no arterial line is present, pulse oximetry may be used.
- o. Female subjects of childbearing potential must have a documented negative pregnancy test at the Screening Visit. Female subjects may be enrolled on the basis of a negative urine pregnancy test, pending the result of a negative serum pregnancy test prior to randomization. A pregnancy test will also be performed on Day 22 or ET (if applicable). Additional pregnancy testing may occur throughout the duration of the study, per applicable country requirements.
- p. Blood samples for chemistry, hematology, and coagulation will be obtained on Days 2 (+1 day), 4 (± 1 day), and 6 (± 1 day) of the Monitoring Period, and twice weekly during Week 2 (Day 8 through Day 14) and/or Week 3 (Day 15 through Day 21) of the Monitoring Period while the subject remains hospitalized.
- q. To be obtained if clinically indicated.
- r. Urinalysis to be obtained on Day 6 (± 1 day) of the Monitoring Period only.
- s. Procalcitonin testing to occur on the day of diagnosis of pneumonia, if applicable.
- t. If applicable.
- u. A chest X-ray or thoracic CT scan is to be obtained 1 time at the initial Screening Visit. A chest X-ray or thoracic CT scan obtained as part of standard of care within 24 hours prior to the initial Screening Visit is sufficient provided there are no changes in the subject's clinical status (e.g., no change in ventilation status, secretions, or signs/symptoms that may be suggestive of pneumonia) within the 24 hours following imaging.
- v. A chest X-ray or thoracic CT scan obtained within 24 hours of the Randomization Visit is sufficient, provided there are no changes in the subject's clinical status (e.g., no change in ventilation status, secretions, or signs/symptoms that may be suggestive of pneumonia) since the time of imaging.
- w. A chest X-ray or thoracic CT scan is required during the Monitoring Period for those subjects presenting with signs and symptoms of a respiratory infection such as dyspnea, tachypnea, fever, or cough.
- x. ETA specimens collected during Screening/Enrollment will be cultured by quantitative or semi-quantitative methods as required by the protocol. Sites are encouraged to perform semi-quantitative cultures using a chromogenic media that tests for both the presence of MSSA and MRSA (e.g., CHROMagar™ *Staph aureus*) for more rapid and specific detection of *S. aureus*. If the site is not able to obtain chromogenic media for *S. aureus*, appropriate chromogenic media may be supplied by the Sponsor. Semi-quantitative cultures using chromogenic media are preferred for determination of eligibility for randomization; however, any quantitative or semi-quantitative culture performed that indicates that a subject is heavily colonized with *S. aureus* is permitted if the culture results are available to randomize the subject within 48 hours (or up to 60 hours with Medical Monitor approval) from the time the ETA sample was collected. If subjects are extubated and subsequently re-intubated/mechanically ventilated, they are eligible for re-screening as a new subject enrollment. Subjects who were previously randomized are not eligible to be re-consented and re-screened. Subjects with a screening ETA culture that also shows heavy colonization of a Gram-negative organism (i.e., heavy co-colonization of both Gram-positive and Gram-negative organisms), will not be randomized into the study; however, randomization should not be delayed while waiting for Gram-negative results if heavy colonization with *S. aureus* has been confirmed.
- y. Adequate respiratory specimen or other microbiological specimens to be obtained if clinically indicated. If, as part of routine standard of care, additional respiratory and/or other microbiological specimens are collected for culture during the study, results will be documented within the eCRF.
- z. Obtain sample for ADA (to be obtained only upon discharge from the ICU, if discharge occurs prior to Day 22).

- aa. Study drug will be administered in a double-blind manner. Subjects will receive ASN100 or matching placebo via 2 IV infusions over a duration of approximately 50 to 60 minutes per infusion. Both ASN100 and placebo will be administered as 2 separate infusions (either sequentially or simultaneously). The last infusion will be completed within 5 hours from initiation of drug preparation in the pharmacy.
- bb. Obtain BAL fluid 48 hours (± 36 hours) post-dose to determine ASN-1 and ASN-2 levels and blood to ELF ratio. If BAL fluid is collected as part of a standard of care procedure from any subject enrolled in the sub-study at any other time post-randomization for any other reason, if possible, a sample for PK analysis will also be obtained.
- cc. Blood samples for PK analysis will be collected immediately following the completion of the second infusion (+15 minutes) and at 6 hours (± 4 hours) and 24 hours (± 6 hours) post-dose.
- dd. Obtain a blood sample for PK measurement ± 1 hour relative to BAL fluid collection (including scheduled BAL fluid collection or if BAL fluid is collected as part of a standard of care procedure from any subject enrolled in the sub-study at any time post-randomization).
- ee. A PK sample will be obtained from all subjects on Days 4 (± 1 day), 7 (± 1 day), 14 (± 2 days), and 22 (+2 days) of the Monitoring Period. Additional PK samples will be collected on the day of discharge (if discharge occurs between Day 40 and Day 90).
- ff. Adverse events that occur between the time the subject signs the ICF and the Randomization Visit will only be recorded if related to a study-specific procedure.

ADA = anti-drug antibody; BAL = bronchoalveolar lavage; CT = computed tomography; ECG = electrocardiogram; eCRF = electronic Case Report Form; ELF = epithelial lining fluid; ET = Early Termination; ETA = endotracheal aspirate; ICF = Informed Consent Form; ICU = intensive care unit; IV = intravenous; MRSA = methicillin-resistant *S. aureus*; MSSA = methicillin-susceptible *S. aureus*; PK = pharmacokinetic; *S. aureus* = *Staphylococcus aureus*; Unsched = unscheduled.

4.4. Selection of Study Population

Male and female subjects 18 years of age who are heavily colonized with *S. aureus* as determined by either quantitative or semi-quantitative culture of an ETA specimen, mechanically ventilated, and, in the Investigator's opinion, will require ongoing ventilator support for at least 48 hours, will be enrolled.

4.5. Randomization and Blinding

Randomization will occur at the Randomization Visit following determination of the subject's eligibility. Subjects will be randomized via a centralized Interactive Response Technology (IRT) system in a 1:1 ratio to receive a single dose (2 infusions) of either ASN100 or matching placebo. Randomization will be stratified by receipt or non-receipt of concomitant anti-staphylococcal antibiotics at the time of randomization that are potentially effective for the treatment of *S. aureus* pneumonia.

The study follows a double-blind, placebo-controlled design. All study personnel, including investigators, site personnel, site pharmacist, Sponsor and contract research organization (CRO) staff involved in the conduct of the study (e.g., clinical research associate [CRA]/monitor), and subjects will be blinded to treatment assignment, except as described below. ASN100 and placebo will be identical in appearance to preserve blinding.

Randomization data will be kept strictly confidential until the time of unblinding and will not be accessible by subjects, Investigators, or anyone performing assessments and having access to study data until unblinding occurs. An independent Data Review Committee (as described in Section 7.6) will conduct a single interim analysis of futility assessment and will receive unblinded study data. Sponsor and CRO staff who are involved in the conduct of the study will not have access to unblinded Data Review Committee materials. The details of the interim analysis are described in the Data Review Committee Charter dated 8-June-2018. Individual subject unblinding will only occur in the case of subject emergencies or as required by regulations when reporting serious unexpected suspected adverse reactions (SUSARs), with complete unblinding at the conclusion of the study.

Emergency breaking of the assigned treatment code should only be undertaken when it is essential that knowledge of the treatment assignment is necessary to treat the subject's emergency safely and effectively. Emergency treatment code breaks will be performed using the IRT. When the Investigator contacts the system to break a treatment code for a subject, he/she must provide the requested subject's identifying information and confirm the necessity to break the treatment code for the subject. The Investigator will then receive details of the investigational drug treatment for the specified subject and a fax or email confirming this information. The system will automatically inform the Sponsor and Medpace study personnel that the code has been broken.

Should the assignment of the subject be needed to fulfill regulatory reporting requirements for SUSARs as noted above, the person designated at the CRO/Sponsor for unblinding needed to fulfill regulatory reporting requirements should contact IRT, for the study drug information. The IRT documentation indicating the blind break at the site, must be retained

with the subject's source documentation in such a way as to avoid unblinding the treatment assignment to other site or Sponsor blinded personnel.

5. STUDY METHODS

5.1. Analysis Populations

The following analysis populations will be used for analyses.

5.1.1. Intent-to-Treat Population (ITT)

The ITT Population includes all subjects who are randomized to receive study drug.

5.1.2. Modified Intent-to-Treat Population (MITT)

The MITT Population includes all subjects in the ITT Population who receive study drug and who are heavily colonized with *S. aureus* as determined by quantitative or semi-quantitative culture of an ETA specimen. Exclusion from the MITT Population will be determined programmatically for each ITT subject. Programmatically determined assignment into the MITT Population will be evaluated for confirmation or Sponsor Override as applicable during a Review Meeting of the Population and Outcome Plan (POP) Review Group, as described in the POP.

Review Meetings will be held on a regular basis throughout the conduct of the study. The number of subjects included in each Review Meeting will vary depending on the number of subjects included in a data review cycle per the Medpace Rolling Data Lock Plan.

The final MITT Population classification will be performed in a blinded fashion and prior to final database lock and unblinding. After the Review Group's review, any Sponsor overrides of the MITT Population flags will be finalized and documented. The MITT Population flags and the reasons for Sponsor Override will also be included in the analysis datasets.

5.1.3. Per Protocol (PP) Population

The PP Population includes all subjects in the MITT Population who also meet the following criteria:

- Did not have any major protocol violations that would affect assessment of efficacy,
- Randomized in a timely manner following collection of an ETA specimen showing heavy *S. aureus* colonization;
- Was mechanically ventilated at randomization;
- Had an appropriate chest image performed at randomization;
- Did not have a change of oxygenation and onset of purulent secretions at randomization;
- Was not diagnosed with pneumonia at randomization or within 24 hours of receiving study drug;
- Received an adequate dose of study drug administered in a timely manner following study drug preparation,

- Did not die within 24 hours of receiving study drug,
- Did not have Investigator Diagnosis of Pneumonia within 24 hours of receiving study drug, and
- Complete an adequate number of Monitoring Period assessments through Day 22 based on medical review of available data.

Exclusion from the PP Population will be determined programmatically for each MITT subject. Programmatically determined assignment into the PP Population will be evaluated for confirmation or Sponsor Override as applicable during a Review Meeting.

The final PP Population classification will be performed in a blinded fashion and prior to final database lock and unblinding. After the Review Group's review, any Sponsor Overrides of the PP Population flags will be finalized and documented. The PP Population flags and the reasons for Sponsor Override will also be included in the analysis datasets.

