#### Per Protocol (PP) Population

The PP Population includes all subjects in the MITT Population who also meet the following criteria:

- Do not have any major protocol violations that would affect assessment of efficacy, and
- Complete an adequate number of Monitoring Period assessments through and including Day 22.

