5.2.5. Secondary Efficacy Endpoints

The secondary efficacy endpoints are:

- Duration of mechanical ventilation during the first 21 days post-randomization for subjects in the MITT, ITT, and PP Populations;
- Length of ICU stay during the first 21 days post-randomization for subjects in the MITT, ITT, and PP Populations;
- The C_{max} , T_{max} , AUC, and $t_{1/2}$ of ASN-1 and ASN-2 in serum following a single dose of ASN100 in the PK Population; and
- 28-day all-cause mortality in the MITT, ITT, and PP Population.

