7.11.2. Additional Analyses for *S. aureus* Pneumonia

Analyses of the primary efficacy endpoint will also be performed based on the ITT and PP Populations.

The following additional analyses will be performed in the MITT and PP Populations:

- The primary efficacy analysis, based on comparing two proportions of subjects who develop *S. aureus* pneumonia by SDO2 up to, but not including, Day 22. If subjects discontinued from the study due to any cause prior to Day 22 it will be considered as not developing *S. aureus* pneumonia for this analysis by SDO2.
- The primary analysis is based on comparing two proportions of subjects who develop *S. aureus* pneumonia by SDO1 up to, but not including, Day 22. For each arm, the empirical proportion is defined by a ratio, which is the number of *S. aureus* pneumonia events divided by the total number of subjects in the arm. The inference about the difference of two population rates is based on the empirical counterpart. Specifically, the point estimate, 95% confidence interval and p-value for the rate difference. If subjects discontinued from the study due to any cause prior to Day 22, it will be considered as developing *S. aureus* pneumonia by SDO1 and SDO2.
- The Kaplan-Meier analysis will be performed for the proportion of subjects who develop *S. aureus* pneumonia by Day 21 as determined by SDO1. The proportion of subjects who develop *S. aureus* pneumonia up to but not including Day 22 will

be obtained from Kaplan-Meier estimates for each treatment group. The inference about the difference of two rates will be made via the Kaplan-Meier estimates and their corresponding variance estimates in the MITT population. The treatment difference of two rates, the corresponding 95% confidence intervals and p-value will be presented. In addition, the number and percentage of subjects who developed *S. aureus* pneumonia or were censored will be summarized. The Kaplan-Meier estimate of event rates evaluated at Day 21 and the corresponding 95% confidence intervals will be presented for each treatment group. Subjects who did not develop *S. aureus* pneumonia, discontinued from the study, or died prior to Day 22 will be considered censored. For the censored subjects, the last assessment date on which the subject did not develop *S. aureus* pneumonia based on the Investigator's assessment will be used as the date of censoring.

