7.11.3. Secondary Efficacy Endpoints

Duration of mechanical ventilation and length of hospital ICU stay during the first 21 days post-randomization will be summarized descriptively and compared between treatment groups using a Wilcoxon rank sum test in the MITT, ITT, and PP Populations.

The other secondary endpoint, 28-day all-cause mortality in the ITT, MITT and PP Population, will be descriptively summarized by treatment group. All-cause mortality rate at Day 28 based on Kaplan-Meier estimates along with the 95% confidence interval will also be presented for each treatment group. Subjects whose survival status are unknown

due to early termination or who are lost to follow up will be censored at the last day the subject was known to be alive.

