7.11.4. Exploratory Efficacy Endpoints

Exploratory efficacy endpoints include:

- Proportion of subjects in the ITT, MITT and PP Populations with a diagnosis of HABP >48 hours post-extubation up to, but not including, Day 22 in extubated subjects;
- Proportion of subjects in the ITT, MITT and PP Populations with development of VABP up to, but not including, Day 22;
- Incidence of all bacterial pneumonias up to, but not including, Day 22 in the MITT, ITT, and PP Populations;
- Incidence of other non-*S. aureus* pneumonias up to, but not including, Day 22 in the MITT, ITT, and PP Populations; and
- Incidence of other *S. aureus* infections acquired up to, but not including, Day 22 in the MITT, ITT, and PP Populations.
- Mechanical ventilation free days and ICU free days during the first 21 days, or prior to death, or early termination post randomization will be summarized descriptively and compared between treatment groups using a Wilcoxon rank sum test in the MITT, ITT, and PP Populations.
- Summary of pneumonia free days for subjects with *S. aureus* pneumonias, for subjects with bacterial pneumonias, and for subjects with any pneumonia in the MITT and PP Populations.
- Summary of All-cause mortality rate at Day 28 for subjects with any pneumonia in the MITT and PP Populations.

All exploratory efficacy endpoints will be descriptively summarized by treatment group.

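### The per-protocol set excludes deaths within 24 hours of dosing, yet 28-day all-cause mortality is reported in that set, so the per-protocol mortality figure is biased low by rule

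*SAP*

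**What the plan says.** SAP 5.1.3 defines PP as MITT subjects who meet a list of further criteria. Two of them bear on survival after dosing:

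- The subject "Did not die within 24 hours of receiving study drug".
- The subject must "Complete an adequate number of Monitoring Period assessments through Day 22 based on medical review of available data".

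Protocol 10.1 has the second in slightly different form ("Complete an adequate number of Monitoring Period assessments through and including Day 22") and does not have the first. SAP section 9, which lists departures from the protocol, does not mention the added criterion. Under SAP 5.1.3 the PP flag is first set by program and then confirmed or overridden in blinded review before database lock.

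Protocol 7.2 lists 28-day all-cause mortality as a secondary endpoint in MITT, ITT and PP, and SAP 5.2.5 repeats it: "28-day all-cause mortality in the MITT, ITT, and PP Population". SAP 7.11.3 gives the analysis: "The other secondary endpoint, 28-day all-cause mortality in the ITT, MITT and PP Population, will be descriptively summarized by treatment group", with a Kaplan-Meier rate and 95% confidence interval per arm. No between-arm mortality test is planned. SAP 7.11.4 adds an exploratory table: "Summary of All-cause mortality rate at Day 28 for subjects with any pneumonia in the MITT and PP Populations".

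**The concern.** Membership of an analysis set should not depend on the outcome being measured in it. Here a death at hour 20 counts towards 28-day mortality in ITT and MITT. In PP the subject is removed from both the numerator and the denominator. The Kaplan-Meier estimate cannot recover the death, because the subject never enters the PP risk set.

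The PP mortality rate is therefore too low in any arm that loses such a subject. If the arms lose different shares of their deaths, the between-arm contrast moves as well, in either direction. Blinded flag review prevents deliberate selection. It does not remove the bias from conditioning on survival after dosing.

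The completeness criterion adds uncertainty. It sets no threshold and does not say how a death or an earlier pneumonia event is handled, so it could in principle remove later deaths too.

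**Working it through.** **The plan's own figures.** The documents give no mortality rate and no expected PP size. The one relevant figure is 152 evaluable subjects per arm (SAP section 6), used below only as a denominator. It reproduces with the pooled-variance formula, two-sided 0.05, 80% power, no continuity correction: (1.960 × √(2 × 0.1875 × 0.8125) + 0.8416 × √(0.25 × 0.75 + 0.125 × 0.875))² / 0.125² = 151.9, so 152. Also 304 / 0.86 = 353.5, so 354. The point does not touch the sample size.

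**Formula.** Let m be the true 28-day mortality and f the share of 28-day deaths removed from PP. Then

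PP mortality = m(1 − f) / (1 − mf).

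For any f above 0 and m below 1 this is less than m, so the direction is certain. The size depends on m and f, and both are assumptions.

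**Only 24-hour deaths removed (the written rule).**

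| True m | f = 2% | f = 5% | f = 10% |
|---|---|---|---|
| 15% | 14.7% | 14.4% | 13.7% |
| 20% | 19.7% | 19.2% | 18.4% |
| 25% | 24.6% | 24.1% | 23.1% |
| 30% | 29.6% | 28.9% | 27.8% |

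For example, 0.25 × 0.95 / (1 − 0.25 × 0.05) = 0.2375 / 0.9875 = 24.1%. With 152 subjects and m = 25% there are 38 deaths, of which 5% is 1.9 subjects.

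Is f near 5% reasonable? Under a constant death hazard, h = −ln(1 − m)/28 per day, and the share of 28-day deaths in the first day is (1 − e^(−h))/m. For m = 25%, h = 0.01027 and the share is 0.01022 / 0.25 = 4.1%. For m = 15% and 30% it is 3.9% and 4.2%.

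**Effect on the contrast under the written rule.** Take a true 25% on placebo and 20% on ASN100 (−5.0 points).

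- f = 3% in both arms: 24.4% v 19.5%, or −4.9 points.
- f = 5% on placebo and 0% on ASN100: 24.1% v 20.0%, or −4.1 points.

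**If the completeness criterion also removed later deaths (not stated in the plan).** For m = 25%:

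- f = 40%: 0.15 / 0.90 = 16.7%.
- f = 80%: 0.05 / 0.80 = 6.25%.

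With f = 80% in both arms, 25% v 20% shows a difference of −1.5 points. With 80% on placebo and 70% on ASN100 it shows +0.7 points, a reversed sign.

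**Which case do the documents support?**

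- SAP 5.1.3 asks for an adequate number of assessments, judged medically. It does not ask for all of them and does not mention death.
- If that criterion excluded every death before Day 22, the separate 24-hour death criterion would have nothing to do.
- SAP 7.11.2 opens with "The following additional analyses will be performed in the MITT and PP Populations". Under that heading it counts discontinuation before Day 22 as an event in one analysis, and in another censors subjects who died or discontinued before Day 22. Both presume that such subjects can be in PP.
- SAP 7.11.3 censors mortality at early termination for all three populations, PP included.
- SAP 7.11.4 truncates ventilator-free and ICU-free days at death or early termination, again with PP among the populations.

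The written 24-hour rule is therefore certain. The wider removal is possible, but the rest of the SAP reads against it.

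**The case against.** The strongest defence has three parts, and most of it stands.

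First, very few deaths should fall within 24 hours. Protocol exclusion criterion 11 and randomization criterion 4 screen out subjects not expected to survive 72 hours, so f may be below the constant-hazard 4%. This stands, and it is why the effect is called small.

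Second, no conclusion rests on PP mortality. ITT and MITT have no exclusion for death after dosing and count every one of these deaths. The mortality summary is descriptive in all three populations, and the primary analysis is in MITT. This also stands.

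Third, review rules sit partly in the Population and Outcome Plan, which is not among the documents reviewed and may say how deaths are treated. So it cannot be claimed that reviewers have no instruction. But the 24-hour rule is in the SAP itself, and a rule elsewhere would not reconcile it with a PP mortality endpoint.

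A reader might go further and infer that PP drops everyone who dies or stops assessments before Day 22. Under constant hazard, that would make true mortality of 15% to 30% read as 4.0% to 8.5% (1 − (1 − m)^(7/28)). The documents do not support this reading, for the reasons set out in the working, and those figures should not be quoted as the size of the problem. Nor is the mortality endpoint as a whole stripped of its deaths; only its PP version is affected.

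**Conclusion.** The point holds in a limited form. By a rule that appears only in the SAP, the PP summary of 28-day mortality omits deaths within 24 hours of dosing and is biased low. With assumed true mortality of 15% to 30% and 5% of deaths removed, the understatement is about 0.6 to 1.1 percentage points (15% reads 14.4%; 30% reads 28.9%). The exploratory Day 28 mortality table for subjects with pneumonia has the same flaw in its PP half.

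A larger bias depends on the completeness criterion being applied to later deaths. The wording leaves room for that, but the SAP's other PP analyses suggest it is not meant. The gap is worth closing because a supportive mortality table should not depend on an unstated judgement. ITT and MITT mortality, the MITT primary analysis and the sample size are not affected.

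**What to change.** 1. In SAP 5.2.5 and 7.11.3, drop PP from 28-day all-cause mortality and rely on ITT and MITT, or do not apply the 24-hour death criterion for that endpoint. Dropping PP is the cleaner choice: a waiver needs a second PP flag and leaves the other post-dose criteria in force, such as pneumonia within 24 hours of dosing. Make the same choice for the PP half of the pneumonia mortality table in SAP 7.11.4.
2. In SAP 5.1.3, judge completeness of assessments only up to the earliest of first SDO1 event, death or Day 21. Then neither a death nor a prior event by itself removes a subject from PP.
3. Record both changes in SAP section 9, together with the 24-hour criterion itself if it is kept for other endpoints.

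Cost: SAP wording and the programmed PP flag, with no new data. SAP section 3 allows modification before unblinding. Either PP becomes slightly larger and less complete, or one supportive table is lost. Changing the protocol text as well would need an amendment under Protocol 13.1; an entry in SAP section 9 records the departure without one.
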